#### **10.6.2 General guidelines for reporting adverse events**

- All AEs, regardless of seriousness or relationship to IMP/NIMP, spanning from the signature of the informed consent form until the end of the study as defined by the protocol for that patient, are to be recorded on the corresponding page(s) or screen(s) of the e-CRF.
- Except for IARs, whenever possible, diagnosis or single syndrome should be reported instead of symptoms. For IARs, all symptoms must be separately recorded.
- The investigator should specify the date of onset, intensity, action taken with respect to IMP, corrective treatment/therapy given, additional investigations performed, outcome, and his/her opinion as to whether there is a reasonable possibility that the AE was caused by the IMP.
- The investigator should take appropriate measures to follow all AEs until clinical recovery is complete and laboratory results have returned to normal, or until progression has been stabilized, or until death, in order to ensure the safety of the patients.
- When treatment is prematurely discontinued, the patient's observations will continue until the end of the study as defined by the protocol.
- Laboratory, vital signs or ECG abnormalities are to be recorded as AEs only if:
  - Symptomatic and/or
  - Requiring either corrective treatment or consultation, and/or
  - Leading to IMP discontinuation or modification of dosing, and/or
  - Fulfilling a seriousness criterion, and/or
  - Defined as an AESI (see [Section 10.6.1.3](#))

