1.1 STUDY DESIGN AND RANDOMIZATION

This is a Phase 1/2, multi-center, open-label, ascending dose study to evaluate the safety, tolerability, pharmacokinetics (PK), pharmacodynamics (PD) and exploratory efficacy of olipudase alfa in pediatric patients less than 18 years of age with non-neuronopathic acid sphingomyelinase deficiency (ASMD). At least 12 patients were initially planned to be enrolled in 3 age cohorts with a minimum of 3 patients aged from 12 to <18 years (adolescent cohort), a minimum of 3 patients aged from 6 to <12 years (child cohort), and at least 2 patients aged from birth to <6 years (infant/early child cohort). At least 8 additional pediatric patients <12 years will be enrolled following protocol amendment 04 (dated 21-Aug-2017). There will be at least 20 patients enrolled in the study in total.

For each patient, study participation will consist of a screening/baseline period (up to 60 days) and a 64-week treatment period with intravenous (IV) infusions of olipudase alfa administered every 2 weeks for 64 weeks. Patients will go through a dose escalation period with target dose of 3.0mg/kg; for further details see protocol Section 1.1.

Eligible patients may enroll in a long-term study (LTS13632) following completion of the 64-week treatment period to continue receiving olipudase alfa. Patients not enrolling in the long-term study will undergo a final safety follow-up assessment by telephone 30 to 37 days after the last infusion in this study; patients with a treatment gap between the end of the 64-week treatment period of DFI13803 and enrollment in the long-term study, depending on the length of the gap, may also undergo a final safety follow-up assessment by telephone 30 to 37 days after the last infusion in this study.

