2.4 EXTENT OF STUDY TREATMENT EXPOSURE AND COMPLIANCE

The extent of study treatment exposure will be assessed and will be summarized using safety population. The duration of exposure is defined as the number of weeks between first infusion and disposition date (ie, the end of study date) in the study: (disposition date of the study – first infusion date + 1)/7. The number of infusions received and the duration of exposure will be summarized by age cohorts and overall.

The distribution of weeks on study treatment (<12 weeks, >=12 weeks to <26 weeks, >=26 weeks to <38 weeks, >=38 weeks to <52 weeks, >=52 weeks to <64 weeks, and >=64 weeks) will be provided using number and percentage of patients by age group cohorts and overall.

Compliance to the treatment regimen will be monitored in terms of the percentage of scheduled infusions the patient receives during the treatment period. A patient is considered noncompliant if the patient missed 2 or more consecutive infusions (not-for-cause, such as when the missed infusions are required by the protocol due to a dose limiting toxicity) or a total of 4 or more infusions for the 64-week treatment period. Whether a missed infusion is for-cause or not will be reviewed and determined by the clinical team; the decision will be used in the analysis of compliance.

Overall Compliance = $100\% \times \text{Total number of infusions received} / \text{Total number of expected infusions}$

where total number of expected infusions refers to the number of infusions expected between the first infusion and the date of withdrawal or date of completion. It is calculated as the integer part of (Date of withdrawal – Date of the first infusion)/14. For a patient who completes the 64-week treatment period, the total number of expected infusions is 33.

Compliance excluding for-cause = $100\% \times \text{Total number of infusions received} / \text{Total number of expected infusions (excluding for-cause missing infusions)}$

where total number of not-for-cause expected infusions refers to the number of infusions expected between the first infusion and the date of withdrawal or date of completion, excluding the

for-cause missed dose. It is calculated as the integer part of [(Date of withdrawal – Date of the first infusion)/14] – number of for-cause missed infusions.

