2.6.1 Adverse events

2.6.1.1 Definitions

AEs are defined in protocol Section 10.6.1. AEs will be coded according to the version of Medical Dictionary for Regulatory Activities (MedDRA) in use at the time of database lock. Adverse event summaries will include the number of events (N), number (n) and percentage (%) of patients experiencing an adverse event. The denominator for computation of percentages is the safety population for the entire study and for each age group cohort. Sorting order will follow the

internationally agreed MedDRA system organ class (SOC) order, then by decreasing number of patients overall in preferred terms (PTs) within SOCs, and further alphabetically within the same number of patients over different PTs. When more than one PT has same number of events within the same SOC, the order of presentation will be alphabetical in PTs.

The AEs will be classified into different periods of occurrence as follows:

- Pre-treatment adverse events: AEs that started before the start of the first infusion.
- TEAEs: AEs that started during the on-treatment period.

If an AE date/time of onset is incomplete, an imputation algorithm will be used to classify the adverse event within the appropriate adverse event period. The algorithm for imputing date/time of onset will be conservative and will classify an adverse event as treatment emergent unless there is definitive information to determine otherwise. Details on classification of AEs with missing or partial onset dates are provided in [Section 2.11.2](#). If an AE worsens in severity, only the worst severity is captured on the AE log page in the e-CRF.

The AE log page in the e-CRF captures the date when the event became serious. If and when this date is non-missing, it indicates that the AE started as non-serious and became serious after few days. To account for non-serious and serious parts of the AE collected in one AE log page, this AE will be split into two AEs – one non-serious, and one serious AE – with the same AE number, with the following modifications in data for these two AEs:

- Non-serious AE: AE end date, AE outcome, date of death or hospitalization, autopsy information, criterion for serious adverse event (SAE) will be blank.
- Serious AE: AE start date will use the date the event became serious.

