Action taken towards study drug and action taken (toward AE) will be considered in relation to the date the event became serious, the last infusion date and dosing information, and a determination will be made, in consultation with safety monitor of the trial, as to whether the recorded fields belong to non-serious AE or serious AE; then the decision will be implemented in analysis. Any such decision will be rationalized in the CSR.

The primary focus of adverse event reporting will be on treatment-emergent adverse events. Pre-treatment adverse events will be listed separately.

Start day of a pre-treatment AE = Start date of AE – first infusion date.

Start day of treatment emergent AE relative to first infusion = Start date of AE – first infusion date + 1.

Start day of treatment emergent AE relative to last infusion = Start date of AE – last infusion date + 1.

2.6.1.2 *Treatment-emergent adverse events*

An overview of TEAEs will be provided by age group cohorts and overall to include (potentially related is defined as either 'related' or 'possibly related' as assessed by the investigator):

- TEAEs.
- TEAEs potentially related to study treatment.
- TEAEs by the worst severity.
- TEAEs leading to treatment discontinuation.
- TEAEs leading to study withdrawal.
- TEAEs leading to dose reduction.
- TEAEs leading to study treatment interruption.
- Protocol-defined IARs.
- Algorithm-defined IARs.
- Treatment-emergent serious adverse events.
- Treatment-emergent serious adverse events potentially related to study treatment.
- TEAEs with fatal outcome (Deaths).
- Treatment-emergent pregnancies.
- TEAEs which are considered symptomatic overdose.
- Dose-limiting toxicities (collected in the adverse event log page in e-CRF, see protocol Section 8.3.4.2.1 for details).

The following summaries will be produced by primary SOC and PT, by age group cohorts and overall:

- TEAEs.
- TEAEs by the worst severity (ie, mild, moderate, or severe).
- TEAEs potentially related to study treatment.

The most common TEAEs are defined as those with percentage of events $\geq 2\%$ and number of patients ≥ 2 in all age cohorts combined. The most common TEAEs by SOC and PT will be provided in descending order of overall incidence by age group cohorts and overall.

TEAEs by the latest infusion dose immediately preceding the start of AE will be provided by SOC and PT, by age group cohorts and overall.

2.6.1.3 *Adverse events of special interest*

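### The SAP selects its most common TEAEs by share of events, with no stated denominator, so the table can omit a widespread term and keep one driven by a single patient's repeats

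*SAP*

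**What the plan says.** SAP 2.6.1.2 defines the table in one sentence: "The most common TEAEs are defined as those with percentage of events" of at least 2%, together with a minimum of two patients, counted over all age cohorts combined. Both conditions must be met. The next sentence says that the selected terms, by SOC and preferred term, "will be provided in descending order of overall incidence by age group cohorts and overall".

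SAP 2.6.1.1 sets the general convention for adverse event tables: "Adverse event summaries will include the number of events (N), number (n) and percentage (%) of patients experiencing an adverse event". It adds: "The denominator for computation of percentages is the safety population for the entire study and for each age group cohort". Protocol 11.4.2.1 likewise counts a patient once per event in the incidence tables. Protocol 11.4.2.1.1 tabulates occurrences as a separate count.

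On recording, Protocol 10.6.2 departs from its usual preference for a single diagnosis: "For IARs, all symptoms must be separately recorded".

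SAP 2.6.1.2 also calls for complete TEAE tables by SOC and preferred term: all TEAEs, by worst severity, potentially related, and by preceding dose.

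**The concern.** A reader takes a table of most common adverse events to show what happened to the most patients. Here the percentage that admits a term is worded on events, while the general percentages and the ordering of the table are on patients. The sentence does not name the event denominator.

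Under the literal reading (events for the term divided by all TEAEs), a term's chance of entry depends on how many other events were reported, as well as on its own spread. The total can become large in this trial because infusion-reaction symptoms are recorded one by one over as many as 33 infusions per patient. SAP 2.6.1.1 also splits an event that later becomes serious into two records. The cut-off in events therefore cannot be known until the data are in. A term reported once by many patients can fall below it, while a term reported repeatedly by one patient and once by another clears it.

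Safety is the primary objective, so a table with this label should not leave out terms that affect a quarter or half of the patients.

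**Working it through.** The plan has no figure to reproduce here: no sample size calculation was performed and no event total is projected. The check applies the rule as written.

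**Inputs**
- Patients: 20, the planned minimum (SAP 1.1: "There will be at least 20 patients enrolled in the study in total").
- Infusions per completer: 33 (SAP 2.4: "the total number of expected infusions is 33"). Planned infusions: 20 × 33 = 660.
- Rule: keep a term if (events for the term ÷ total TEAEs) ≥ 0.02 and patients with the term ≥ 2.
- Total TEAEs: **an assumption**, 300 to 1000. Per planned infusion this is 300/660 = 0.45 to 1000/660 = 1.52 events.

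**Literal reading (share of events)**

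The cut-off in events is 0.02 × total. A term reported once per affected patient has as many events as patients, so the widest such term left out is one below the cut-off.

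| Total events | Cut-off (events) | Widest once-per-patient term left out | Its event share | Two-patient term kept |
|---|---|---|---|---|
| 300 | 6 | 5 of 20 (25%) | 5/300 = 1.67% | 5 + 1 |
| 500 | 10 | 9 of 20 (45%) | 9/500 = 1.80% | 9 + 1 |
| 600 | 12 | 11 of 20 (55%) | 11/600 = 1.83% | 11 + 1 |
| 1000 | 20 | 19 of 20 (95%) | 19/1000 = 1.90% | 19 + 1 |

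For a term seen once in half of the patients (10 events), the switch comes at 10/0.02 = 500 events:
- 10/500 = 2.00%: kept.
- 10/501 = 1.996%: left out.
- 500 events are 500/20 = 25 per patient, or 500/660 = 0.76 per planned infusion.

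Comparison at 600 events:
- 10 patients, 10 events: 10/600 = 1.67%, left out.
- 2 patients, 11 + 1 events: 12/600 = 2.00%, kept.
- 1 patient, 17 events: 17/600 = 2.83%, left out, because the two-patient condition fails.

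**Patient reading (denominator of SAP 2.6.1.1)**

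0.02 × 20 = 0.4 patients. The two-patient condition already requires 2/20 = 10%. A 2% criterion would equal two patients only at 2/0.02 = 100 patients. At this trial's size it adds nothing.

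**The case against.** The strongest reply is that little depends on this table. The complete SOC and preferred term tables show every term with its number and percentage of patients and its event count, so nothing is lost from the report. The protocol's own adverse event section does not include a most-common table, and no document calls it the main safety display. This stands, and it limits the point to one descriptive table.

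Second, the event total is assumed. Up to 500 events, a term seen once in 10 of 20 patients is kept. The 95% row needs 1000 events and 19 patients who each report the term exactly once in 64 weeks, which is an extreme case. This also stands: the rule could omit such terms, and the documents do not show that it would.

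Third, a reader might infer that one patient's repeated event can enter the table. It cannot, because the two-patient condition in the same sentence excludes it. The supportable case is a term with a second patient who contributes as little as one event.

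Fourth, a reader might infer that the table would be dominated by a few patients with recurrent reactions. The documents do not support this. Separate recording of symptoms raises the total but spreads it over different preferred terms, and no figure shows events concentrating in a few patients. Ordering by overall incidence would also place a two-patient term low in the table. It does not bring back a term that was left out.

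Finally, the 2% may have been meant on the patient denominator. The table would then list every term seen in at least two patients, and the omission would not arise. The wording favours events, however, and under the patient reading the percentage has no function. The sentence needs correcting either way.

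**Conclusion.** The point holds for this one table. The selection rule uses a share of events with no stated denominator, against the patient-based convention of the section before it.

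Taken literally, with 20 patients and an assumed 300 to 1000 TEAEs, the cut-off is 6 to 20 events. Terms reported once in 25% of patients could be left out at 300 events, and terms reported once in 50% above 500. At 600 events, a two-patient term of 11 + 1 would be kept. Taken on patients, the percentage is redundant at this sample size.

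The illustrations rest on the assumed event total and on terms that occur once per affected patient; repeat occurrences would make a widespread term easier to keep. No test, endpoint or dosing decision depends on the rule, and the full tables remain complete. The correction is worth making because the table could otherwise mislead a reader who relies on its label, and because the change is small.

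**What to change.** Replace the defining sentence in SAP 2.6.1.2 with a patient-based rule: most common TEAEs are preferred terms reported in at least 10% of the safety population, all age cohorts combined (at least 2 of 20 patients). Sort by number of patients overall, and show the number of events in a second column.

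State that the percentage governs if the safety population exceeds 20, which is possible because 20 is a minimum and patients replaced for early intolerance remain in that population. At 21 patients, for example, 0.10 × 21 = 2.1, so three patients would be needed.

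The cost is one sentence and a somewhat longer table. The patient counts, percentages and event counts are already required by SAP 2.6.1.1, so no new data or method is needed.

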Dose regimen	
Olipudase alfa will be administered every 2 weeks for 64 weeks. All patients will receive an initial dose of 0.03 mg/kg olipudase alfa, which will then be followed by one dose of 0.1 mg/kg, and two consecutive doses at 0.3 mg/kg. Patients tolerating 2 consecutive doses of 0.3 mg/kg will be dose escalated step-wise to receive 2 consecutive doses at 0.6 mg/kg, which will be followed by infusions at 1.0 mg/kg and 2.0 mg/kg, and to the final target dose of 3.0 mg/kg, which is to be maintained for the remaining duration of the treatment period. Patients unable to tolerate 3.0 mg/kg olipudase alfa will receive the highest tolerable dose every 2 weeks until the end of the treatment period.
 
Patients unable to tolerate 2 consecutive doses of 0.3 mg/kg olipudase alfa will be replaced.

Noninvestigational medicinal product(s) (if applicable)	Not applicable.
ENDPOINT(S)	
Primary endpoint:
 
Data pertaining to the safety and tolerability of olipudase alfa:
 
 
Assessment of adverse events/treatment-emergent adverse events (TEAEs), including infusion-associated reactions
 
Physical examinations
 
Neurological examinations
 

[figure not shown]

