### **8.3.2 Investigational medicinal product administration**

For all dose levels, dosing with olipudase alfa is by intravenous infusion every 2 weeks ( $\pm 3$  days). The dose escalation phase and the 64-week treatment period begin with the first intravenous infusion of 0.03 mg/kg olipudase alfa on Day 1/Week 0 ([Section 1.1](#)). All subsequent olipudase alfa administrations are to be scheduled relative to the Day 1/Week 0 visit. The dose escalation phase ends with the first infusion at 3.0 mg/kg or with the identification of a patient-specific highest tolerated dose.

Patients who tolerate the 0.03 mg/kg dose at Day 1/Week 0 (one re-challenge of the 0.03 mg/kg dose is allowed) will receive a dose of 0.1 mg/kg 2 weeks later. Patients who tolerate the 0.1 mg/kg dose (one re-challenge of the first 0.1 mg/kg dose is allowed) will receive a dose of 0.3 mg/kg dose 2 weeks later. Patients tolerating 2 consecutive doses of 0.3 mg/kg will be dose escalated step-wise to receive 2 consecutive doses at 0.6 mg/kg, followed by infusions at 1.0 mg/kg and 2.0 mg/kg, and to the final target dose of 3.0 mg/kg, which is maintained for the remaining duration of the treatment period. Patients unable to tolerate 3.0 mg/kg olipudase alfa will receive the highest tolerable dose every 2 weeks until the end of the treatment period. (Refer to [Section 8.3.4.2.1](#) for patient stopping criteria.)

Decisions regarding dose escalations may be made by discussion between the investigator and the sponsor upon review on an individual patient basis. See [Section 8.3.4](#) for dose escalation criteria.

All infusions will take place in a monitored setting with ready access to emergency resuscitation equipment and medications.

Patients will receive intravenous olipudase alfa over a period of approximately 20 minutes to 4.5 hours, depending on the dose. The length of the infusion time may be adjusted based on the patient's tolerance of the infusion.

Infusions should be administered at approximately the same time of the day. There are no restrictions on the infusion timing with respect to meals.

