#### **11.4.2.1 Adverse events**

The definitions in [Section 10.6.1](#) will be used for AEs. Pre-treatment AEs will be listed and presented separately from treatment-emergent AEs.

Adverse events will be coded according to the most recent version of the Medical Dictionary for Regulatory Activities (MedDRA). Adverse event incidence tables will be presented by MedDRA system organ class (SOC) (sorted by internationally agreed order) and preferred term (PT) sorted in decreasing number of patients within SOCs and further alphabetical order within the same number of patients over different PTs for each age group, the number (n) and percentage (%) of patients experiencing an AE. Multiple occurrences of the same event in the same patient will be counted only once in the tables within a treatment period. The denominator for computation of percentages is the safety population for the entire study and each age group cohort.

Adverse events will be classified into pre-defined standard categories according to chronological criteria:

- Pre-treatment AEs: AEs that occurred or worsened during the pre-treatment period;
- Treatment-emergent AEs (TEAEs): AEs that occurred or worsened during the on-treatment period);
- Post-treatment AEs: AEs that occurred or worsened during the post-treatment period.

If the start date of an AE is incomplete or missing, then the AE will be considered as a TEAE unless a partial date shows it as a pre- or post-treatment event.

All AEs reported in the study will be listed, sorted by patient, and onset date.

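### The planned TEAE-by-dose table does not adjust for exposure, so unequal numbers of infusions per dose alone will make 3.0 mg/kg look more toxic

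*SAP*

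**What the plan says.** SAP 2.6.1.2 attributes each event to the dose last given: "TEAEs by the latest infusion dose immediately preceding the start of AE will be provided by SOC and PT", split by age cohort and overall. The sentence names no denominator.

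The general rules in SAP 2.6.1.1 therefore govern. On content: "Adverse event summaries will include the number of events (N), number (n) and percentage (%) of patients experiencing an adverse event". On percentages: "The denominator for computation of percentages is the safety population for the entire study and for each age group cohort". Protocol 11.4.2.1 has the same denominator rule.

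On exposure, SAP 2.4 states: "For a patient who completes the 64-week treatment period, the total number of expected infusions is 33". It summarises infusions received and duration of exposure by age cohort and overall, not by dose.

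The regimen is in the Protocol's Clinical Trial Summary and Section 8.3.2: one infusion at 0.03 and one at 0.1 mg/kg, two at 0.3, two at 0.6, then 1.0, 2.0 and the 3.0 mg/kg target, "which is to be maintained for the remaining duration of the treatment period". On the interval: "For all dose levels, dosing with olipudase alfa is by intravenous infusion every 2 weeks".

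**The concern.** Attribution to the latest dose gives each dose a period at risk that lasts until the next dose level starts. For a single-infusion dose this is about two weeks. For 3.0 mg/kg it is the rest of the study. Ordinary childhood illness, unrelated to dose, will therefore collect in the 3.0 mg/kg column. Neither the event count nor the patient percentage corrects for this, and no visible summary table gives infusions by dose from which a reader could correct it.

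The primary objective is safety and tolerability, and the study escalates dose within patients. A reader will go to this table to ask whether toxicity rises with dose. Two errors are possible: seeing a dose trend that is only exposure, or failing to notice a true excess during escalation. The second matters here because Protocol 6.4 calls escalation the most critical phase for safety. It also reports that the two dose modifications in the adult Phase 1b study followed moderate infusion-associated reactions at 1.0 and 2.0 mg/kg, which are single-infusion doses in the present schedule.

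**Working it through.** **1. Reproduce the SAP's figure.** Infusions at Weeks 0, 2, …, 64 number 64/2 + 1 = 33, which matches SAP 2.4.

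**2. Infusions by dose, uninterrupted escalation.** Weeks 0 to 14 take 1 + 1 + 2 + 2 + 1 + 1 = 8 infusions (0.03, 0.1, 0.3, 0.6, 1.0 and 2.0 mg/kg). The first 3.0 mg/kg infusion falls at Week 16. That leaves 33 − 8 = 25 at 3.0 mg/kg, or 25/33 = 75.8%. Protocol 10.3.4 fits this timing: it allows for the first 1.0 mg/kg infusion at Week 12.

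**3. Percentage of patients with at least one event under flat risk.** Assume the same risk p after every infusion, independent between infusions. The documents give no p, so a range is shown. The formula is 1 − (1 − p)^k, with k infusions at the dose.

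| p | k = 1 (0.03, 0.1, 1.0, 2.0) | k = 2 (0.3, 0.6) | k = 25 (3.0) | Ratio 25:1 |
|---|---|---|---|---|
| 1% | 1.0% | 2.0% | 22.2% | 22.2 |
| 2% | 2.0% | 4.0% | 39.7% | 19.8 |
| 5% | 5.0% | 9.8% | 72.3% | 14.5 |
| 10% | 10.0% | 19.0% | 92.8% | 9.3 |
| 20% | 20.0% | 36.0% | 99.6% | 5.0 |
| 50% | 50.0% | 75.0% | 100% | 2.0 |

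For p = 5%: 1 − 0.95^25 = 72.3%. Expected event counts stand at 25 to 1 (or 25 to 2) whatever p is.

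**4. Relax the assumptions, at p = 5%.**
- Fewer infusions at 3.0 mg/kg: k = 20 gives 64.2%, k = 15 gives 53.7%, still against 5%.
- Clustering within patients (beta-binomial, correlation 0.3): 27.0% at k = 25, against 5.0% at k = 1 and 8.3% at k = 2.

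**5. Masking.** A risk of 40% at the single 1.0 mg/kg infusion would show as 40% of patients. A 2% per-infusion risk at 3.0 mg/kg would show as 39.7%. The two columns would look alike, although the per-infusion risks differ 20-fold.

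**6. Effect of the denominator taken alone.** With p = 5% and 2 of 20 treated patients never reaching 3.0 mg/kg, the table shows 72.3% × 18/20 = 65.0%, against 72.3% of those exposed. The safety-population denominator lowers the 3.0 mg/kg figure.

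**7. After the fix.** With 20 completers and p = 5%, expected events per infusions given are 1/20 at each single-infusion dose, 2/40 at 0.3 and at 0.6 mg/kg, and 25/500 at 3.0 mg/kg. Every dose shows 5 per 100 infusions, as it should when risk is flat.

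**The case against.** Several points on the other side are sound.

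- **The denominator is inferred.** The by-dose sentence does not state one, and the general rule does not mention dose columns. Applying that rule is the natural reading, but it is a default and not an explicit choice for this table.
- **The denominator is not the cause.** A reader might infer that counting the whole safety population makes 3.0 mg/kg look worse. Step 6 shows the reverse. Unequal exposure drives the inflation, and restricting the denominator to exposed patients would by itself widen the gap slightly.
- **This is not the only look at dose and toxicity.** A reader might infer that it is. Protocol 11.4.2.7 summarises safety biomarkers by highest tolerated dose, and Protocol 11.4.6 allows exposure-response work with safety biomarkers. SAP 2.6.1.2 counts dose-limiting toxicities and TEAEs leading to dose reduction or interruption. SAP 2.6.1.9 is redacted. What can be said is that this is the only visible AE table by dose; the infusion-reaction tables in SAP 2.6.1.3 split by severity and timing.
- **Escalation doses are not concealed.** Each has its own column, and with one infusion per patient the percentage there is close to a per-infusion risk. Among escalation doses exposure differs at most 2 to 1. The misleading comparison is with 3.0 mg/kg.
- **Twenty-five is a planned maximum.** Repeats and missed infusions reduce it. A patient whose highest tolerated dose is below 3.0 mg/kg adds maintenance infusions to a lower column instead.
- **The table is descriptive.** No test is attached, and the listings would let someone compute rates later.

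These points limit the cause, the scope and the size. They do not remove the problem: the summary table as specified cannot separate dose from number of infusions.

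**Conclusion.** The point holds as a matter of interpretation. Under the general AE rules, the by-dose TEAE table compares a column with up to 25 infusions per patient against columns with 1 or 2, without adjustment. With flat, independent per-infusion risks of 2%, 5% and 10%, the 3.0 mg/kg column would show about 40%, 72% and 93% of patients, against 2%, 5% and 10% at single-infusion doses. These are illustrations, not predictions: the risks are assumed, infusions are taken as independent, and escalation is taken as uninterrupted. Clustering, repeats and missed infusions all reduce the gap. It is largest, in relative terms, for preferred terms with low per-infusion risk, and about 2-fold in patient percentage when that risk is near 50%.

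A secondary fault is that patients who never reach a dose stay in its denominator. Protocol 11.4.2 confirms that the safety population includes those withdrawn for intolerance of 0.1 or 0.3 mg/kg. This slightly understates the percentages at higher doses.

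Error rates are unaffected. Because safety is the primary objective and the remedy is nearly free, the table should be corrected.

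**What to change.** In SAP 2.6.1.2, specify the by-dose TEAE table as follows, overall and by age cohort:

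1. Show the number of patients exposed and the number of infusions given at each dose.
2. Use patients exposed at that dose as the percentage denominator.
3. Add events per 100 infusions at that dose, or per unit of patient-time.
4. Show the proportion of patients with a TEAE after their first infusion at each dose and before the next infusion. This compares one infusion per patient at every level, and prevents a pooled 3.0 mg/kg rate from diluting early events at that dose.

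Item 2 alone does not correct the exposure imbalance; items 3 and 4 do. None of the four separates dose from treatment order, because every patient escalates in the same sequence. A footnote should say so.

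The cost is a few lines of SAP text and a few extra columns. Infusion and dose records are already collected, and no new data are needed.
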